### 6.5. Per Protocol Set

The per protocol set (PPS) is a subset of the FAS; the PPS will exclude subjects with protocol deviations that may significantly impact the assessment of the primary objective of the study. Analyses in the PPS will be based on the study treatment actually received by each subject. All decisions to exclude subjects from the PPS will be made prior to the unblinding of the study.

[figure not shown]
### 6.6. Pharmacokinetic Set

The PK analysis set will consist of all subjects who were correctly administered at least 1 ME3183 dose and where ME3183 or CCI concentration data is available without any protocol deviation interfering with these results. Analyses in the PK analysis set will be based on the study treatment actually received by each subject. In the event of drug mis-dispensation when a subject has received more than one active study drug, the subject will be excluded from the PK analysis set.

PK concentrations are listed for all subjects in PK analysis set.

This document is confidential.

CCI

## 6.8. Protocol Deviations

All subject data will be reviewed for the occurrence of protocol deviations. Identified protocol deviations will be recorded into the Clinical Trial Management System (CTMS) by the Site Monitor. The detail on the types of Protocol deviation criteria is made in the BDRM Preparation Plan. Final decisions of subjects to be included in the PPS will be made at the BDRM. All deviations will be categorized as major or minor. Significant protocol deviations are defined as those with major severity.

Deviation type will be recorded as one of the following categories:

- Concomitant Medication / Administration of prohibited medication
- Inclusion or Exclusion Criteria
- Informed Consent / ICF not signed or signed late
- Informed Consent / Other
- Investigational Product / Incorrect IP kit given to subject
- Investigational Product / IP
- Investigational Product / IP Storage
- Investigational Product / Other
- Met Withdrawal Criteria but was not Withdrawn
- Randomization / Mis-stratification
- Randomization / Multiple Randomizations
- Randomization / Other
- Randomization / Randomized not Treated
- Randomization / Treated and not Randomized
- SAE not reported or reported late
- Study Procedure / Missed procedure

*This document is confidential.*

- Study Procedure / Other
- Study Procedure / Site Staff Authorization, Delegation, Training
- Study Procedure / Subject compliance
- Study Procedure / Unmasking (not per protocol)
- Study Procedure / Visit Missing
- Visit Window

This document is confidential.

## 7. Estimands

### 7.1. Estimand for Primary Efficacy Endpoint

The main estimand for the primary efficacy endpoint 'proportion of subjects achieving  $\geq 75\%$  reduction from baseline in the PASI score (PASI-75) at Week 16' is defined as follows:

- Population: Subjects with moderate to severe plaque psoriasis defined by the study inclusion/exclusion criteria in [Section 4.2](#). The analysis population for the primary efficacy endpoint will be full analysis set as defined in [Section 6.2](#) and per protocol set as defined in [Section 6.3](#).
- Variable: Binary variable indicating whether the subject has achieved  $\geq 75\%$  reduction from baseline in the PASI score (PASI-75) at Week 16.
- Population-level summary: Numbers and proportions of subjects achieving  $\geq 75\%$  reduction from baseline in the PASI score (PASI-75) at Week 16, and differences in these proportions between each ME3183 treatment group and placebo group.
- Intercurrent events:
  - Withdrawals or early terminations will be handled using hypothetical strategy, where Last Observation Carried Forward (LOCF) and Non-responder Imputation (NRI) will be applied as sensitivity analyses in addition to complete-case analysis.
  - All other intercurrent events will be handled using treatment policy strategy.

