- subject fails to adhere to the protocol requirements (eg, drug noncompliance, failure to return for defined number of visits, used or require to use any of the prohibited concomitant medication or procedures [see [APPENDIX 2](#)])
- lost to follow-up: the subject stopped coming for visits, and study personnel are unable to contact the subject
- subject has any other factor constituting disqualification for study inclusion in the judgement of the investigator

- pregnancy, as indicated in [Section 12.6.6](#).

Additionally, the Sponsor may stop the study at any time for safety, regulatory, legal, or other reasons aligned with Good Clinical Practice (GCP). This study may be terminated at the discretion of the Sponsor or any regulatory agency. An investigator may elect to discontinue or stop the study at his or her study site for any reason, including safety or low randomization.

Withdrawn subjects may not be replaced once randomized.

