APPENDIX 2. PROHIBITED CONCOMITANT MEDICATIONS AND PROCEDURES

The following concomitant medications and procedures are prohibited prior to randomization and during the course of the study unless otherwise specified.

1. Topical therapy:

Topical therapy unless otherwise specified (including but not limited to topical corticosteroids, topical retinoid [tazarotene] or vitamin D analogue preparations [calcipotriene and calcitriol], tacrolimus, pimecrolimus, methoxsalen, trimethylpsoralen, pimecrolimus or anthralin/dithranol). Topical therapy is prohibited from 2 weeks prior to the first administration of study treatment until 4 weeks after the last dose of study treatment unless otherwise specified in [Section 9.6.1](#).

2. Systemic therapy:

Systemic therapy including but not limited to oral or injectable retinoids, apremilast (or any other PDE4 inhibitors), acitretin, methotrexate, cyclosporine, corticosteroids, mycophenolate mofetil, 6-thioguanine, hydroxyurea, thioguanine, sirolimus, isotretinoin, sulfasalazine, azathioprine, or fumaric acid esters are be prohibited from 4 weeks prior to the first administration of study treatment until 4 weeks after the last dose of study treatment.

CCI

3. Biologic Agents:

- Tumor necrosis factor (TNF)- α inhibitors (certolizumab pegol, etanercept, adalimumab, infliximab, and golimumab) are prohibited from 8 weeks prior to the first administration of study treatment until 4 weeks after the last dose of study treatment.
- TNF- α inhibitor, rituximab, is prohibited from 24 weeks prior to the first administration of study treatment until 4 weeks after the last dose of study treatment.
- Interleukin (IL)-12/23 inhibitors (ustekinumab or any other therapeutic agent targeting IL-12 or IL-23) is prohibited from 24 weeks prior to the first administration of study treatment until 4 weeks after the last dose of study treatment.
- IL-17 inhibitors (secukinumab, ixekizumab, brodalumab, or any other therapeutic agent targeting IL-17) are prohibited from 24 weeks prior to the first administration of study treatment until 4 weeks after the last dose of study treatment.

- IL-23 inhibitors (tildrakizumab, risankizumab, guselkumab, or any other therapeutic agent targeting IL-23) are prohibited from 24 weeks prior to the first administration of study treatment until 4 weeks after the last dose of study treatment.

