### 6.4. Full Analysis Set

All subjects who have been randomized, received at least 1 dose of study drug, and have at least 1 evaluable post-baseline time point for primary endpoint will be included in the full analysis set (FAS). Analyses in the FAS will be based on the subject's randomized treatment group.

The FAS will be used for all analyses of efficacy endpoints.

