### 10.1. Primary Efficacy Endpoint and Analysis

The primary efficacy endpoint is the proportion of subjects achieving  $\geq 75\%$  reduction from baseline in the PASI score at Week 16. Baseline is defined as the PASI score on Day 1 pre-dose.

For each ME3183 treatment group, the difference in the proportion of subjects achieving the difference in PASI-75 (ME3183 – placebo) and its 95% confidence interval (CI) will be estimated and tested for superior treatment effect using the Cochran-Mantel-Haenszel (CMH) test with prior receipt of any biologics for psoriasis (bio-naïve vs non-bio-naïve) as adjustment factor at a 1-sided significance level of  $\alpha = 0.025$ .

Analysis will be conducted using observed data at Week 16 only (complete-case analysis). In the presence of missing data, additional sensitivity analysis will be conducted using both LOCF and NRI. Under LOCF, the last non-missing PASI score will be carried forward to Week 16, based on which the subject will be considered as responder or non-responder and summarized accordingly. Under NRI, subjects with missing PASI scores at Week 16 will be considered non-responders.

Subgroup analysis will be carried out stratified by the prior receipt of any biologics for psoriasis (bio-naïve vs non-bio-naïve), where Fisher's exact test will be used instead of CMH for superiority.

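### A subject who takes prohibited psoriasis therapy, is not withdrawn and has an observed Week 16 PASI-75 is a responder in all three FAS analyses, NRI included

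*SAP*

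**What the plan says.** **Strategies.** SAP Section 7.1 deals with two kinds of intercurrent event for the primary endpoint. For the first, "Withdrawals or early terminations will be handled using hypothetical strategy", with LOCF and NRI beside the complete-case analysis. For the rest, "All other intercurrent events will be handled using treatment policy strategy". Prohibited therapy is not named, so it belongs to the rest.

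**Analyses.** SAP Section 10.1 bases the main analysis on observed Week 16 data. The two sensitivity analyses act only on missing scores: "Under LOCF, the last non-missing PASI score will be carried forward to Week 16", and "Under NRI, subjects with missing PASI scores at Week 16 will be considered non-responders". SAP Section 10.2 uses the same logic for PASI at the other visits and lists LOCF and NRI for the sPGA response.

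**Analysis sets.** The FAS (SAP Section 6.4) has no exclusion for prohibited therapy: "Analyses in the FAS will be based on the subject's randomized treatment group". The PPS (SAP Section 6.5) excludes deviations that could materially affect the primary objective, decided before unblinding.

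**Prohibited therapy.** Protocol Appendix 2 opens: "The following concomitant medications and procedures are prohibited prior to randomization and during the course of the study unless otherwise specified". Its list covers topical, systemic, biologic and light therapy. Protocol Section 8.4 includes, among the reasons for which a subject may leave or be withdrawn, that the subject "used or require to use any of the prohibited concomitant medication or procedures".

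**The concern.** The responder definition looks only at the Week 16 PASI. Eligibility criteria 26 and 28 of the protocol describe the systemic and topical treatments concerned as ones that could alter psoriasis or its assessment. If a subject takes one, stays in the study and then meets PASI-75, the response may belong to the other therapy, yet it is credited to the randomized arm.

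The planned sensitivity analyses do not test this. Complete-case, LOCF and NRI differ only in what they do with a missing score. None varies the treatment-policy assumption.

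Comparable subjects can also be scored differently. Protocol Section 7.2 says a subject with an unbearable flare can leave and receive other treatment. With no Week 16 score, that subject is dropped from the complete-case analysis and failed under NRI. A subject who takes such treatment and stays can be a success in both.

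At stake is whether any FAS analysis in this proof-of-concept study shows response without credit for another psoriasis treatment.

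**Working it through.** **Step 1. Trace the rule.**

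| Subject takes prohibited psoriasis therapy and... | Complete-case | LOCF | NRI | PPS |
|---|---|---|---|---|
| stays; Week 16 PASI observed, PASI-75 met | responder | responder | responder | may be removed; not a failure |
| leaves; Week 16 PASI missing | dropped | last score decides | non-responder | may be removed |

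The gap is the first row. In the second row only LOCF can keep a response recorded after the other therapy. One case is unsettled: Visit 8 assessments are also done at early termination (Protocol Section 7.4) and SAP Section 8.4 uses visits as recorded. An early-termination PASI stored as Visit 8 could therefore place a withdrawn subject in the first row.

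**Step 2. Inputs from the documents.** 25 randomized per arm in five arms (5 × 25 = 125, as stated); assumed drop-out 10%; one-sided α = 0.025, each dose against placebo. No response rates, effect size, power or rate of prohibited use is given, so there is no planned figure to reproduce. All rates below are assumptions.

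**Step 3. Shift per subject.** 1/25 = 4.0 points. With 10% drop-out, 25 × 0.9 = 22.5 completers, so 1/23 = 4.3 to 1/22 = 4.5 points.

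**Step 4. Effect on one comparison.** Mantel-Haenszel statistic without the prior-biologic strata, a drug and b placebo responders, m = a + b, N = 50:

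Z = (a − m/2) / √[25·25·m·(50 − m) / (50²·49)]

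For 9 against 3: m = 12, variance = 625·12·38/122,500 = 2.327, Z = 3/1.525 = 1.967.

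| Assumed responders | Change | Z | One-sided p |
|---|---|---|---|
| 9/25 v 3/25 | none | 1.967 | 0.0246 |
| 8/25 v 3/25 | one drug responder reclassified | 1.690 | 0.0455 |
| 9/25 v 2/25 | one placebo responder reclassified | 2.366 | 0.0090 |
| 8/25 v 2/25 | none | 2.100 | 0.0179 |
| 7/25 v 2/25 | one drug responder reclassified | 1.822 | 0.0342 |
| 8/25 v 1/25 | one placebo responder reclassified | 2.551 | 0.0054 |

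**Step 5. Both directions.**

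*Use on placebo only.* Power = Φ{[√25·(pₐ − pₚ) − 1.96·√(2p̄(1 − p̄))] / √[pₐ(1 − pₐ) + pₚ(1 − pₚ)]}. At 40% against 10%: (1.5 − 1.200)/0.574 = 0.522, power 69.9%. If other therapy adds 4 or 8 points to placebo, power is 54.6% or 40.0%.

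*Use on drug only, drug without effect.* Summing the binomial probabilities of all outcomes with Z ≥ 1.96, at a true rate of 10% in both arms, gives a rejection probability of 2.4%. If the drug arm gains 4 or 8 points from other therapy, it is 6.5% or 13.0%.

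**Step 6. What the PPS does.** If one of 9 drug responders is removed, the arm is 8/24 = 33.3%; counted as a failure, it is 8/25 = 32.0%. The point estimates are close. But removal is not assured (SAP Section 9.2 says a major deviation may lead to it), and the PPS also removes subjects for unrelated deviations, so it does not isolate this effect.

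**The case against.** **Treatment policy is a legitimate, explicit choice.** This stands. Nothing here makes the primary analysis wrong, and a reader who infers that goes beyond the documents.

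**The case is narrow.** This also stands. One might infer that every user of prohibited therapy can be a success in all three analyses; only a user with an observed Week 16 score can. Nor does the word may in Protocol Section 8.4 show that users are meant to stay: the same list contains pregnancy, for which Section 8.4.1 requires withdrawal from treatment. But no comparable requirement is stated for prohibited therapy, and SAP Section 6.8 has a deviation category for subjects who met withdrawal criteria and were not withdrawn. The case is foreseen, without a responder rule.

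**Safeguards exist.** Prohibited medication is a named deviation, major deviations are tabulated by category and arm, and the PPS repeats the PASI and sPGA response analyses with complete-case, LOCF and NRI. The detailed deviation criteria are in a separate blind-review plan that is not among the documents. This is a relevant check, with the limits in Step 6.

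**The direction is not known.** It is tempting to infer that flares drive other therapy mainly on placebo, so that the drug effect is understated. No passage supports this. More use on drug would overstate it.

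**Not all use signals treatment failure.** A systemic corticosteroid may be taken briefly for another illness. A rule failing every later visit after any use would misclassify genuine responders, so the rule must consider indication, timing and type.

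**Conclusion.** The point holds for a subject who takes prohibited psoriasis therapy, is not withdrawn and has an observed Week 16 PASI-75. That subject is a responder in all three FAS analyses, and the PPS can only take the subject out of the denominator.

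The size is unknown. It is about 4 points per subject at 25 per arm, and zero if there is no such use. Under the assumed counts in Step 4, one subject can carry a comparison across 0.025 in either direction when the result is near the threshold. Those figures rest on assumed responder counts, no missing data and an unstratified test.

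This is a cheap improvement to the sensitivity analyses of a Phase 2a study with no formal sample size. It is not a defect in the primary analysis.

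**What to change.** 1. Keep treatment policy for the primary complete-case analysis.
2. In SAP Sections 10.1 and 10.2, define the NRI analyses of PASI-50/75/90/100 and the sPGA 0/1 response so that non-response is assigned when the score is missing, and also at any visit whose score could be affected by psoriasis therapy prohibited in Appendix 2.
3. Flag those visits at the blind data review from the recorded indication, dates and type of therapy. Leave out the topicals permitted in Protocol Section 9.6.1 and any use judged unable to affect the score at that visit.
4. Report the number reclassified per arm, separately from those failed for a missing score, so that the two reasons are not merged.
5. Amend SAP Sections 7.1 and 7.2 to name this as a composite-strategy sensitivity estimand. Section 7.2 needs its own sentence: it has no clause for events other than withdrawal, and it describes the PASI and sPGA imputation analyses as hypothetical.

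The withdrawal and prohibited-therapy rules in the protocol are not touched. The cost is SAP wording and one flag, settled before unblinding. Protocol Section 9.6.1 already requires indication and dates of use in the eCRF, and the blind review is already planned. Downsides: NRI response rates may be slightly lower, and the flag needs blinded judgement.

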### 7.2. Estimands for Secondary Efficacy Endpoints

The estimands for secondary efficacy endpoints are defined as below:

- Population: Subjects with moderate to severe plaque psoriasis defined by the study inclusion/exclusion criteria in [Section 4.2](#). The analysis population for the secondary efficacy endpoints will be full analysis set as defined in [Section 6.2](#).
- Variables:
  - Continuous variables measuring the percent changes from baseline in PASI score at all visits from Week 1 to Week 16
  - Binary variables indicating whether the subject has achieved  $\geq 50\%$ ,  $75\%$ ,  $90\%$  and  $100\%$  reduction from baseline in the PASI score at all visits from Week 1 to Week 16
  - Time to event variable measuring the time from baseline to the time achieving  $\geq 50\%$  and  $75\%$  reduction in PASI score in days respectively, censored by the date of last PASI assessment date for subjects who never achieves  $\geq 50\%$  or  $75\%$  reduction
  - Binary variables indicating whether the subject has achieved a sPGA score of "0" ("clear") or "1" ("almost clear") combined with a 2-point reduction on the 5-point sPGA scale at all visits from Week 1 and Week 16
  - Continuous variables measuring the changes from baseline in BSA at all visits from Week 1 to Week 16
  - Continuous variables measuring the changes from baseline in NRS at all visits from Week 1 to Week 16
  - Continuous variables measuring the changes from baseline in DLQI score at all visits from Week 1 to Week 16

This document is confidential.

- Binary variables indicating whether a subject achieves at least a 5-point reduction from baseline in the DLQI score at all visits from Week 1 to Week 16
- Population-level summary:
  - Binary variables will be summarized using numbers and proportions of subjects achieving that outcome of interest, then differences in the proportions between each ME3183 treatment group and placebo group will be calculated.
  - Continuous variables will be summarized using descriptive statistics by treatment group and overall. Mixed-effect model for repeated measures will be used to estimate the least-square (LS) mean differences between each ME3183 treatment group and placebo group.
  - Time to event variables will be summarized using medians and 95% CIs, Kaplan-Meier estimates, and hazard ratios estimated Cox proportional hazard models.
- Intercurrent events:
  - Withdrawals or early terminations will be handled via while-on-treatment policy, where no missing data will be imputed, except for analyses listed below where intercurrent events will be handled via hypothetical strategy and missing data will be imputed using LOCF and NRI methods in addition to complete case analysis: percent change from baseline for PASI scores at all visits from Week 1 to Week 16, the numbers and percentages of subjects achieving  $\geq 50\%$ , 75%, 90% and 100% reduction from baseline in the PASI score at all visits from Week 1 to Week 16, the numbers and percentages of subjects achieving an sPGA score of "0" ("clear") or "1" ("almost clear") and a 2-point reduction from baseline.

### 7.3. Estimands for Secondary Safety Endpoints

The estimands for the secondary safety endpoints are defined as below:

- Population: Subjects with moderate to severe plaque psoriasis defined by the study inclusion/exclusion criteria in [Section 4.2](#). The analysis population for the secondary safety endpoints will be the safety analysis set as defined in [Section 6.1](#).
- Variables:
  - Binary variables indicating whether a subject experiences any AEs over the 16-week treatment period and the 4-week follow-up period, along with information regarding severity and seriousness
  - Continuous variables measuring the change from baseline in CS physical examination findings and vital sign measurements (blood pressure, heart rate, respiratory rate, body temperature, and body weight) over the 16-week treatment period and the 4-week follow-up period
  - Continuous variables measuring the change from baseline in ECG findings over the 16-week treatment period and the 4-week follow-up period
  - Binary variable indicating whether the subject has any abnormal ECG findings at all visits over the 16-week treatment period and the 4-week follow-up period
  - Continuous variables measuring the change from baseline in safety laboratory values (hematology, coagulation, blood chemistry and urinalysis) over the 16-week treatment period and the 4-week follow-up period
  - Binary variables indicating whether subject has any abnormal safety laboratory findings (hematology, coagulation, blood chemistry and urinalysis) over the 16-week treatment period and the 4-week follow-up period

This document is confidential.

- Population-level summary:
  - Binary variables will be summarized using numbers and proportions of subjects achieving that outcome of interest.
  - Continuous variables will be summarized using descriptive statistics.
- Intercurrent events:
  - Withdrawals or early terminations will be handled via while-on-treatment policy, where no missing data will be imputed.

This document is confidential.

## 8. General Aspects for Statistical Analysis

### 8.1. General Methods

- Unless otherwise specified, summaries will be presented for each treatment group and overall.
- Continuous variables will be summarized using the number of subjects (N), mean, standard deviation (SD), median, minimum, and maximum. Categorical variables will be tabulated with the number and percentage of subjects for each category.
- All relevant subject data will be included in listings. All subject data will be included in listings. The listings will be generally sorted by treatment and subject identification (ID), unless otherwise specified.

